Osseous Paget's disease is a very rare disease in Japan and available drugs are limited compared with Europe and the U.S. Benet 17.5 mg Tablets (this drug) was designated as an orphan drug and developed for treatment of osseous Paget's disease. During development, patients with osseous Paget's disease were surveyed for 40 weeks after oral administration of one tablet of this drug once daily for 8 consecutive weeks (total of 48 weeks). High level of serum alkaline phosphatase (serum ALP) that indicates abnormal acceleration of bone metabolism turnover, was lowered and maintained during the observation period. With respect to safety, a serious adverse event was observed in one patient (recurrent cholangiocarcinoma) but causal relationship was denied. However, osseous Paget's disease is rare disease in Japan and only a very limited number of patients (12 patients) were reviewed.

The purpose of this special drug use surveillance (8-week treatment period) is to evaluate the safety and efficacy of this drug administered once daily (one tablet per dose) in patients with osseous Paget's disease for 48 weeks from baseline in daily medical practice.

This surveillance is conducted as an all-case surveillance based on the approval conditions of this drug.

<Approval conditions>

“Given that the number of study patients is very limited in Japan, a drug use surveillance in all patients should be conducted after marketing until data are accumulated from a certain number of patients to understand the background information of the patients treated with this drug and to promptly collect the data of safety and efficacy of this drug, and to take necessary actions for ensuring appropriate use of this drug.”

2. Scheduled number of patients and justification

(1) Scheduled number of patients

All patients (all patients administered this drug)

(2) Justification

This is an all-case surveillance in all patients administered this drug, and all patients are included in the survey without determining the number of patients.

3. Targeted patients

(1) Targeted patients

Osseous Paget's disease patients

(2) Dosage and administration in targeted patients

The usual dosage for adults is 17.5 mg of sodium risedronate administered orally with a sufficient volume (approximately 180 mL) of water once daily after waking for 8 consecutive weeks.

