		
• 5.(4)9) correction of treatment compliance• 5.(5)1) correction of changes in excess serum ALP• 5.(5)2) correction of changes in excess serum ALP (subgroup analysis)• 5.(5)4) correction of changes in serum ALP• 5.(5)5) correction of changes in serum ALP (subgroup analysis)

Table of Contents

1. Purpose of analysis	1
2. Patients to be included in analyses	1
(1) Breakdown of patients to be included in analyses	1
(2) Patients included in safety evaluation	1
(3) Patients included in efficacy evaluation	1
3. Handling of patients	1
4. Data Lock Point	2
(1) Data Lock Point	2
5. Tabulation and analysis at each DLP	2
(1) Patient composition diagram	2
(2) Details of patients excluded from safety evaluation and patients excluded from efficacy evaluation	2
(3) Details of discontinued/dropout patients	3
(4) Safety analysis	3
(5) Efficacy analysis	9
(6) Analysis of patients excluded from safety evaluation	13
(7) List of summary of surveyed patients (Attachment form 3)	13
(8) Other arrangements	13

Terminology

Term	Explanation
Adverse event	All events recorded in [Adverse events] section of CRF. All untoward medical events encountered in a patient administered a medication (including abnormal laboratory data and infections). A causal relationship with this drug is not always clear.
Adverse drug reaction	Adverse events with “causal relationship with this drug” in [Adverse events] section of case report form (CRF) other than “not related”. However, an adverse event judged by the investigator as “not related” but judged by the sponsor as “related” is handled as an adverse drug reaction.
Serious adverse event	Adverse event for which “seriousness” in [Adverse events] section of CRF is “serious”. However, an adverse event judged by the investigator as “non-serious” but judged by the sponsor as “serious” is handled as a serious adverse drug reaction. Also, adverse events listed in the implementation guide as an “adverse event to be always judged serious” and “Takeda Medically Significant AE List” are included as well.

1. Purpose of analysis

To determine tabulation and analysis that are conducted for preparation of the documents for application for reexamination and a periodic safety report in the survey conducted for the following purpose.

[Purpose of survey]

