Prepare according to (Note) 1 to 7 in Attachment form 2 of PFSB/ELD Notification No. 1027004 of Director of Pharmaceutical Evaluation Division dated October 27, 2005. Attach a list of adverse drug reactions/infections by patient unit to the far right of this table.

Prepare a list of onset of adverse drug reactions according to administration category (initial administration, re-administration 1, re-administration 2, re-administration 3 onward) and treatment period (≤ 56 days, ≥ 57 days, unknown) in the same manner shown in Attachment form 2.

Accumulation and total section in (Note) 2

- The same site participating in Ph 2 and Ph 3 is counted once concerning the number of surveyed sites up to approval.
- A report submitted by the same site for the first and second reporting is counted once concerning

cumulative total section for the number of surveyed sites.

- A report submitted from the same site prior to approval and during a special drug use survey is counted once concerning a total section of a number of surveyed sites.

Number of occurrences of same adverse drug reactions/infections encountered in the same patient in (Note) 3

- In tabulation of SOC, several occurrences of the same SOC in a given patient is counted once.
- In tabulation of PT, several occurrences of the same PT in a given patient is counted once.

Infections in (Note) 7

- No infection was collected or reported by the time of obtaining approval.

Percentage (%) of number of onset (occurrence) of adverse drug reactions by types in (Note) 7

- Calculate percentage (%) for the number of patients by types (occurrences) to the second decimal place (round up to the second decimal place). The same is applied hereinafter unless otherwise stated.

3) List of occurrences of serious adverse events (Attachment form 10 of the notification of Director of Ministry of Health, Labour and Welfare)

<Analysis population>

Patients included in safety evaluation.

<Preparation method>

Prepare according to (Notes) 1 to 8 in Attachment form 10 of PFSB/ELD Notification No. 1027004 of Director of Pharmaceutical Evaluation Division dated October 27,2005. Present serious adverse events by patient unit at the far right of this table.Cumulative total and total section in (Note) 3

- The same site that participates in Ph 2 and Ph 3 studies is counted once concerning the number of surveyed sites up to approval.

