- A report submitted by the same site for the first and second reporting is counted once concerning cumulative total section for the number of surveyed sites.
- A report submitted from the same site prior to approval and during a special drug use survey is counted once concerning a total section of a number of surveyed sites.

Number of adverse events encountered in the same patient in (Note) 4

- In tabulation of SOC, several occurrences of the same SOC in a given patient is counted once.
- In tabulation of PT, several occurrences of the same PT in a given patient is counted once.

4) List of seriousness, date of onset, outcome of adverse drug reactions

<Analysis population>

Patients included in safety evaluation.

<Preparation method>

Tabulate seriousness, date of onset, and outcome of adverse drug reactions by types according to the category in the following table (2). Adverse drug reactions will be handled according to the “2) List of onset of adverse drug reactions/infections (Attachment form 2 of the notification from director of MHLW)”. However, in case of several occurrences of adverse drug reactions classified into the same PT in a given patient, select the most serious for seriousness, initial onset for the date of onset of adverse drug reactions, and the severest outcome.

Seriousness: serious>non-serious

Time of onset: event with earlier onset

Outcome: death> recovered with sequela> not recovered> improved> recovered >unknown

Prepare a list of adverse drug reactions according to administration category (initial administration, re-administration 1, re-administration 2, re-administration 3 onward) and treatment period (≤ 56 days, ≥ 57 days) in the same manner

Table (2) Category of seriousness, date of onset, and outcome

Item	Category
Seriousness	1) serious, 2) non-serious, 3) unknown
Timing of onset ^{*1}	1) Day 1 - 7, 2) Day 8 - 14, 3) Day 15 - 21, 4) Day 22 - 28, 5) Day 29 - 56, 6) Day 57 - 84, 7) Day 85 - 180, 8) Day 181 - 210, 9) Day 211 - 360, 10) Day 361 onward, 11) unknown
Outcome	1) recovered, 2) improved, 3) not recovered, 4) recovered with sequela, 5) death, 6) unknown

*1: number of days counted from the “date of starting administration” as “Day 1” until “date of onset of adverse drug reactions”.

5) Onset of adverse drug reactions by factors

<Analysis population>

Patients included in safety evaluation.

<Preparation method>

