All patients in spontaneous reporting, literature, drug use surveillance, special drug use survey, clinical trials, post-marketing clinical trials, and a clinical trial conducted by other pharmaceutical company.

<Preparation method>

Concerning serious adverse drug reactions, number of patients will be calculated for each type of adverse drug reactions (according to SOC and PT) by the timing of onset and outcome category shown in Table (2). In case of several occurrences of the same adverse event/adverse drug reaction (LLT) in a given patient, they will be tabulated as one according to the priority order in 4). Events with the same PT but different LLT will be tabulated as separate events.

11) Profile table of adverse drug reactions not foreseeable from “Precautions”

<Analysis population>

All patients in spontaneous reporting, literature, drug use surveillance, special drug use survey, clinical trials, post-marketing clinical trials, and a clinical trial conducted by other pharmaceutical company.

<Preparation method>

Concerning the adverse drug reactions not foreseeable from “Precautions”, number of patients for each types of adverse drug reactions (SOC, PT) will be calculated based on the categories of seriousness, timing of onset, and outcome shown in Table (2). In case of several occurrences of the same adverse event/adverse drug reaction (LLT) in a given patient, they will be tabulated as one according to the priority order in 4). Events with the same PT but different LLT will be tabulated as separate events.

(5) Efficacy analysis

1) Changes in excess serum ALP

<Analysis population>

Patients included in efficacy evaluation. However, patients without baseline data or post-administration data will be excluded.

<Preparation method>

For excess serum ALP, measured value at each time point and percent change from baseline will be calculated and summary statistics and two-sided 95% confidence interval will be shown. A paired t-test will be conducted for percent change and p-value of test results will be shown. Details of handling of data at each time point will be shown in “(8) Other arrangements 5) Data of evaluation time point”.

A graph showing changes in mean \pm standard deviation will be prepared for the measured values at each time point and percent change.

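### The SAP's serious adverse event definition sends sponsor-upgraded events to serious adverse drug reaction with no causality condition, in conflict with its own adverse drug reaction definition

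*SAP*

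**What the plan says.** The Terminology table of SAP Ver. 4.1 has two rows that matter here.

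- **Adverse drug reaction.** The test is causality only: the investigator's CRF entry is anything but not related. An event that the investigator judges unrelated and the sponsor judges related "is handled as an adverse drug reaction".
- **Serious adverse event.** There are three parts. First, the CRF seriousness entry is serious. Second, an event rated non-serious by the investigator and serious by the sponsor "is handled as a serious adverse drug reaction". Third, events on either of two lists (the one in the implementation guide and the sponsor's list of medically significant events) "are included as well".

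Serious adverse drug reaction has no row of its own. Three outputs draw on these terms:

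- 5.(4)3), "List of occurrences of serious adverse events";
- 5.(4)4), "Tabulate seriousness, date of onset, and outcome of adverse drug reactions by types";
- 5.(4)10), "Concerning serious adverse drug reactions, number of patients will be calculated for each type of adverse drug reactions".

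The Terminology table and 5.(4)10) both entered the SAP at Ver. 4.0. The sentence is the same in Ver. 4.0 and Ver. 4.1. Protocol section 7(6) has seriousness and causal relationship recorded as separate items.

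**The concern.** A change in seriousness carries no information about causality. The second part of the Serious adverse event row nevertheless places an event in a causal category on seriousness alone. The row above would exclude the same event if neither the investigator nor the sponsor judged it related.

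The sentence is operative. It is the only Terminology text that assigns events to serious adverse drug reaction, and 5.(4)10) counts patients in that category. That table has its own re-examination data lock point, the 13th. A programmer who looks up the definition of a serious reaction finds this rule and no other. At stake is whether the table contains only events for which someone suspected the drug, and whether the serious adverse event list contains every event that either party called serious.

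**Working it through.** The plan gives no figure to reproduce. The check classifies every possible event under the wording as it stands and under a corrected wording.

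**Inputs.** Five yes/no attributes, all taken from the two Terminology rows: investigator says serious; sponsor says serious; investigator says related (any entry except not related); sponsor says related; event is on either seriousness list. This gives 2 × 2 × 2 × 2 × 2 = 32 combinations. An event is *upgraded* when the investigator says non-serious and the sponsor says serious (8 of the 32). It is a reaction when either party says related.

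**Three rules compared.**

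- *Exclusive literal reading.* An upgraded event is a serious reaction. An event is a serious adverse event only through the CRF entry or a list.
- *Inclusive literal reading.* As above, but an upgraded event also counts as a serious adverse event.
- *Corrected wording.* An upgraded event is a serious adverse event. A serious reaction is an event that is both a reaction and a serious adverse event.

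**Results against the corrected wording.**

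| Reading | Wrongly a serious reaction | Missing from serious adverse events |
|---|---|---|
| Exclusive literal | 2 of 32 | 4 of 32 |
| Inclusive literal | 2 of 32 | 0 of 32 |

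The 2 over-counted combinations are upgraded events that both parties judge unrelated, one on a list and one not. The 4 that can go missing are upgraded events on neither list, one for each of the four causality combinations. Upgraded events that either party judges related are rightly serious reactions under every rule.

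**Size.** The over-count equals the number of upgraded events that both parties judge unrelated. The documents give neither this number nor the number of upgrades, so the following values are assumptions. With U upgraded events, each independently unrelated with probability q, the expected over-count is U × q and the chance of at least one is 1 − (1 − q)^U.

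| U | q | Expected over-count | Chance of at least one |
|---|---|---|---|
| 1, 3 or 5 | 0 | 0 | 0 |
| 1 | 0.5 | 0.5 | 0.50 |
| 3 | 0.5 | 1.5 | 0.875 |
| 5 | 0.5 | 2.5 | 0.969 |
| 1, 3 or 5 | 1 | 1, 3 or 5 | 1 |

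Over these assumptions the expected over-count runs from 0 to 5.

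**Which outputs are exposed.** 5.(4)10) is exposed directly, because it uses the term that the sentence assigns. 5.(4)3) is exposed only on the exclusive reading. 5.(4)4) starts from events already classed as reactions in list 5.(4)2), so it is reached only if the sentence is also taken to amend the adverse drug reaction row.

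**The case against.** The strongest reply is that this is a drafting or translation slip that would not mislead anyone. The sentence follows the pattern of the row above, where the corresponding sentence ends on that row's own term; by the same pattern this one should end on serious adverse event. Other slips of this kind occur, such as the pain categories used to grade imaging findings in 5.(5)9). A programmer might well apply the evident intention. That is plausible, but it supports correcting the text. Nothing elsewhere in the SAP states the intended rule, and the Ver. 4.1 corrections left the sentence alone.

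A reader might infer that upgraded events are lost from the serious adverse event list. The documents do not establish this. The sentence stands inside the Serious adverse event definition, between two other routes into that category, and the SAP treats a reaction as a kind of adverse event. The inclusive reading, with no loss, is at least as natural. 5.(4)3) also follows notes to a ministry form that is not reproduced, so how that form admits events cannot be checked here.

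A reader might also infer that serious reactions are over-counted as a matter of fact. That needs the sentence to override the causality row and at least one upgraded event that both parties judge unrelated. Neither is shown.

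Finally, it is tempting to scale the effect from Protocol section 1, where "a serious adverse event was observed in one patient (recurrent cholangiocarcinoma) but causal relationship was denied" among 12 patients: 1/12 = 8.3% serious reactions instead of 0/12. That does not hold. Nothing says this event became serious through a sponsor upgrade, the 12 patients belong to development and not to this survey, and 5.(4)10) counts patients pooled over several sources without a percentage.

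**Conclusion.** The two Terminology rows contradict each other for a sponsor-upgraded event that neither party judges related, and the sentence is wrong as written. This much rests on the current text alone. The consequences are conditional. If the sentence is applied literally, every patient with such an event could enter the serious adverse drug reaction profile table, 5.(4)10), without any causal suspicion. If it is also read as exclusive, upgraded events on neither list could be absent from 5.(4)3). How many events are affected is unknown and may be zero. The point therefore concerns an internal inconsistency in an operative definition; no bias in the results has been demonstrated. It still deserves correction, because the table concerned supports the re-examination application and in so rare a disease a single misplaced event could be noticeable.

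**What to change.** In the Serious adverse event row, end the second sentence so that the event *is handled as a serious adverse event*. Add a row stating that a serious adverse drug reaction is an event that meets both the serious adverse event and the adverse drug reaction definitions. Under this wording all 32 combinations are classified consistently, with no over-count and no loss.

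Then check the derivation program for 5.(4)3) and 5.(4)10) against the new text. If tables have already been produced, list the sponsor-upgraded events with both causality judgements and their list status. If none was judged unrelated by both parties, and all of them appear in 5.(4)3), record that the correction changes nothing.

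The cost is one changed sentence, one added definition and a short program check. No new data are needed.
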